## **4) STUDY OBJECTIVES**

### **4.1 Primary Question/Objective:**

The primary aim of this study is to develop and begin testing the acceptability and feasibility of a 6-8 session treatment package aimed at improving mind-body integration in a series of people with FND. This will be measured using adherence to therapy, patient satisfaction and acceptability measures.

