### **5.2 Study Intervention and/or Procedures**

Treatment:

- Participants will be offered 8, 1-hour, online sessions, delivered weekly via Microsoft Teams. The intervention will focus on developing skills to improve attunement to the signals from the body to the brain.
- The sessions will involve engaging in various exercises tuning into the body under different circumstances. Participants will be asked to tune into how particular objects feel in their hands. Participants may be presented with short clips or stories to make them feel a little happy or sad and then will be asked to tune into how the body feels in response to them.
- These sessions will be recorded via Microsoft Teams and selected aspects of them will be observed by the principal researcher and their clinical supervisor to ensure therapy quality.
- Participants will be asked to complete weekly measures online via Qualtrics survey platform in the 10-15 minutes prior to their session commencing. Assessment measures (CORE-10, FND symptoms questions, EuroQol Dimension and a measure of adverse reactions to the therapy) will be completed weekly. Any adverse reactions will be addressed in the beginning of the session.
- In the final session of treatment, all the preliminary measures will be repeated along with the measures of satisfaction in therapy and intervention acceptability.
- Following the final session of treatment, a date to complete a one-month follow up will be arranged with the participant.

Follow-Up:

- One month following the end of psychological therapy, a session will be attended remotely via Microsoft Teams by participants.

- During this session, all pre-treatment, weekly and post-treatment measures will be re-administered including questionnaires measuring satisfaction with therapy.

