## **8) DATA COLLECTION, SOURCE DATA AND CONFIDENTIALITY**

Personally identifiable data will be collected about participants including their name, address, contact details, details of registered GP. Data around participants' FND symptoms, mental health and quality of life will also be collected and stored. These will be collected via interview and questionnaires delivered via Qualtrics survey. Treatment sessions will also be audio and video recorded to be monitored for quality in Clinical Supervision.

Therapy sessions will be recorded using Microsoft Teams using the Principal Investigator's University of Manchester Teams account. Following the session, recordings will immediately be transferred on to the principal researcher's University of Manchester secure P-Drive. Recordings will be deleted as soon as possible following the principal researcher receiving clinical supervision on the sessions recorded. Sessions will be stored on a University drive in mp4 format using password protection which will only be known by the research team. The research team will monitor to ensure that videos are password protected and are only being accessed for the purpose of supervision. The password will contain a minimum 7 characters, have a mixture of upper- and lower-case letters, symbols and numbers. The recording will be checked and then deleted from Teams. Consent forms and safety plans will be saved on the Research Data Storage system. The file name will be saved with a date of consent and allocated a number to protect confidentiality and ensure no file names are the same (i.e. DD\_MMM\_YYYY\_P\_1 or DD\_MMM\_YYYY\_CL\_1). Participants will be asked to complete measures throughout baseline, treatment and follow-up. These will be administered via Qualtrics survey. Participants will complete surveys under Unique ID codes and the data received from participants will therefore be stored under their Unique ID codes. Data from Qualtrics surveys will be stored on the P-Drive under the anonymised ID codes.

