## **9) STATISTICAL CONSIDERATIONS**

### **9.1 Statistical Analysis**

To assess the primary aim (acceptability and feasibility), we will measure adherence to treatment, safety (adverse reactions) and attitude to intervention. We will conduct descriptive statistical analysis of: therapy completion rates, sessions attended, measures completed, adverse events and participant satisfaction with the therapy.

In order to assess the secondary hypothesis (efficacy of treatment) we will chart individual participant FND symptoms and clinical measures during the baseline and treatment phases to determine any change in these variables over the course of treatment. We will calculate Rate of Change Index (RCI) and Clinically Significant Change (CSC) for the various outcome measures to determine if the change seen is statistically reliable and clinically meaningful.

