The intervention for the study will be delivered by a Trainee Clinical Psychologist (principal researcher) under the close supervision of the Primary Academic Supervisor (who is a qualified Clinical Psychologist). In the event of a participant experiencing serious adverse reactions to the treatment delivered, a protocol will be activated whereby the research team will consider stopping the trial. The research team will consider withdrawing treatment from participants not experiencing serious adverse reactions following evaluating severity of risks. Decisions around proceeding or stopping the trial will involve an independent academic from within the Division of Psychology and Mental Health at the University of Manchester. Any decisions around stopping the trial will take into account the impact on other participants and risks of this will be mitigated accordingly (through offering additional generic support, signposting to support and alternative non-direct counselling or support). Whilst the principal researcher has developed protocols to manage and mitigate any risks to participants, we have no reason to believe this therapy will carry any higher risk than any other therapy that is regularly offered to individual's with FND. Any adverse event, reaction, serious adverse event or reactions occurring for participants will be logged and documented and the outcome of decision making around each reaction will also be logged and stored in order to monitor the overall wellbeing of participants in the study. The information sheet will also emphasise that the intervention offered is a novel treatment that is aiming to gather initial evidence as

to its effectiveness, this is to fully inform participants of the nature of the intervention being delivered and manage expectations around its effectiveness so that participants can make informed choices around consenting to participate. Furthermore, at the end of the intervention, the principal researcher will discuss future options with participants including signposting to further support services as appropriate.

There is the potential as with any psychological intervention that the principal researcher could become distressed or affected by the delivery of intervention. This will be mitigated by the principal researcher being closely supervised by a qualified Clinical Psychologist throughout the delivery of intervention. No other risks to researchers have been identified

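### Satisfaction and acceptability, two of the primary-aim measures, may be biased upward: they are completed in the therapist's own final session, and nothing keeps individual answers from the therapist

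*Combined protocol and SAP*

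**What the plan says.** Section 4.1 states how the primary aim is judged: "This will be measured using adherence to therapy, patient satisfaction and acceptability measures". Section 9.1 puts it slightly differently, "we will measure adherence to treatment, safety (adverse reactions) and attitude to intervention", and plans a descriptive analysis of "therapy completion rates, sessions attended, measures completed, adverse events and participant satisfaction with the therapy".

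On timing, Section 5.2 says: "In the final session of treatment, all the preliminary measures will be repeated along with the measures of satisfaction in therapy and intervention acceptability". One month after therapy ends, "a session will be attended remotely via Microsoft Teams by participants", and "During this session, all pre-treatment, weekly and post-treatment measures will be re-administered including questionnaires measuring satisfaction with therapy". That last sentence names satisfaction. Acceptability comes in only as one of the post-treatment measures.

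On who does what, Section 6.3 has the principal researcher take consent, and Section 13.2 gives the same person the therapy: "The intervention for the study will be delivered by a Trainee Clinical Psychologist (principal researcher").

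On mode, Section 8 puts the measures at every stage on Qualtrics, and "Participants will complete surveys under Unique ID codes".

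**The concern.** A participant is asked to judge a therapy while in a session with the person who has just delivered it, who took their consent, and whose research project it is. In that position people tend to be kind. Any such pull would favour the intervention, which is also the direction the protocol expects: Section 2 anticipates that the package will prove acceptable.

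Acceptability also carries much of the rationale. Section 3 argues that work on body perception may be better received by patients who can resist psychological accounts of their symptoms. Section 7 says that positive outcomes could inform further research and development of the intervention. If the ratings that speak most directly to this are soft, the case for further work rests partly on politeness.

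**Working it through.** No arithmetic applies. The plan states no acceptability threshold, no proportion to be reached and no error rate, so there is no figure to reproduce. The check is to set the sections side by side.

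1. **What is exposed.** Section 4.1 names three measures: adherence, satisfaction and acceptability. Section 9.1 adds safety and lists completion rates, sessions attended and measures completed. Satisfaction and acceptability are opinions about the therapy. Attendance and completion are counts and much less open to a wish to please. Adverse-reaction reports are a separate matter, because the therapist has to see them at once.

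2. **Where the forms are completed.** Section 5.2 places the weekly measures in the 10-15 minutes before each session begins. It places satisfaction and acceptability inside the final session. So the plan already separates some self-report from the session, but not the two forms for which separation matters most.

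3. **Who is there.** The final session is a treatment session on Microsoft Teams, and Section 13.2 assigns treatment to the principal researcher. Sessions are also recorded, and selected parts are viewed by that person and the clinical supervisor (Section 5.2). For follow-up, no section names who conducts the session.

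4. **Whether the ID codes hide the answers.** Section 8 does not say that they do, and four points suggest otherwise:
   - Weekly adverse-reaction answers are dealt with at the start of the same session (Section 5.2), so the therapist evidently sees answers linked to a person.
   - Survey data are kept on the P-Drive, which Section 8 describes, for the recordings, as the principal researcher's own.
   - Vouchers depend on each person's completion percentage (Section 15), so someone must match codes to people.
   - There are 8 participants and one named therapist.

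5. **Whether the analysis could reveal a bias.** There is one group, no comparator, no independent or anonymous rating, and a descriptive summary. An upward shift shared by all participants would look the same as genuine satisfaction.

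6. **Size.** Estimating the shift would need ratings collected another way, and the plan has none. The direction of the risk can be argued; its magnitude cannot be derived.

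**The case against.** The strongest reply is that the forms are not an interview. They are self-completed online under a code, which takes away some face-to-face pressure, and Section 5.2 does not say that the therapist watches, reads out or discusses them. This stands as mitigation. It falls short of a safeguard, because no section provides for the therapist's absence or for withheld answers.

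The second reply is that the primary aim does not rest on these ratings alone. That is right, and it limits the damage. A reader might infer that the primary outcomes as a whole are compromised. Section 9.1 does not support that, since attendance, completion and adverse events also serve the aim.

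A reader might also infer that the follow-up ratings are given to the therapist. The documents do not name the person who runs that session, so this is a gap to fill and not an established fault.

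It could further be said that forms completed in the last session come before treatment has ended. The repeat of all measures one month later largely answers that.

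Finally, moving forms out of the session has a price. Measures completed is itself a feasibility outcome, and if dissatisfied participants return fewer forms, a favourable bias comes back by another route. Moving the whole post-treatment set would also take CORE-34 away from a scheduled contact. These objections are sound, and they are why the change should be confined to two forms.

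**Conclusion.** The point holds as a risk of upward bias in two of the primary-aim measures. It rests on the final-session sentence in Section 5.2 read with Section 13.2, and on the absence of any provision that keeps individual ratings from the therapist. It assumes that being in session with the therapist, or expecting the therapist to read the answers, can soften a rating. The documents neither show nor rule this out.

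Two stronger readings are tempting and not supported. One is that the ratings will be inflated; the documents allow only that they may be. The other is a numerical effect. Each of 8 participants counts for 1/8 = 12.5 percentage points, so two softened answers would turn 6/8 = 75% satisfied into 8/8 = 100%. That arithmetic shows how coarse a sample of 8 is. The plan defines no satisfied category and no threshold to cross, so it is not an estimate of this bias.

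The point does not undermine the study. It is a cheap improvement to a stated procedure, worth making because the bias could not be found or removed afterwards.

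**What to change.** 1. In Section 5.2, have only the satisfaction and acceptability forms completed alone, by Qualtrics link sent the same day, straight after the final session and again after the follow-up session.
2. In Section 8, restrict individual ratings on these two forms from the therapist until the last participant's follow-up is complete. Give access to an existing team member who does not deliver therapy, who tells the therapist only whether a form has been returned. The academic supervisor could do this. That person is not independent of the therapist, but the purpose is concealment of individual answers, so the ratings should stay out of supervision until they are released.
3. Say this on the form, so that participants know before they answer.
4. Leave the CORE, symptom, risk and adverse-reaction measures where they are and immediately visible.
5. State who runs the follow-up session.
6. Report the remaining limitation: one group, and ratings held within the same team.

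The cost is a change of timing and access rights on a platform already in use, with no added staff. The downside is a few late or missing forms, which would also lower the measures-completed outcome. Same-day links and reminders limit this, as does the existing voucher scale in Section 15, where the £45 voucher requires 100% completion and the next step down is £40. Non-return of these two forms should be reported alongside the ratings, so that selective return can be seen.

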### **5.3 End of study**

The end of the study will be defined as when the last participant has completed their last follow-up session and completed the follow-up measures. At this point, plans that have been approved by the UREC for the use of data collected in the course of the study will be reviewed. Following the study completion, analysis and write-up, the results of the study will be disseminated to the participants that have consented to be contacted for this purpose.

## **6) STUDY PARTICIPANT0053**

### **6.1 Inclusion Criteria:**

Participants will eligible to participate if they:

- Are currently experiencing FND symptoms, as measured on items 34-47 on the SOMS-7 questionnaire (excluding seizures and hallucinations). The study is aiming to investigate the feasibility of an intervention for individuals with FND.
- Have a confirmed diagnosis of FND (through letter from medical doctor) to ensure participants have a diagnosis of FND and are therefore the target audience for the intervention
- Are willing and able to participate in remote therapy. The intervention will be delivered remotely so participants must be willing to engage with remote therapy.
- Are able to converse in English proficiently without support from a link worker. The study will not be using interpreters and so an ability to converse proficiently in English to be able to engage with the intervention is needed.
- Are residing in the UK for the duration of the study, this is so the trial therapist would be able to develop an informed crisis and risk management plan for participants should they experience any negative effects from therapy or express any risks during the course of the intervention.

### **6.2 Exclusion Criteria:**

Participants will not be eligible to participate in the study if they:

- Are currently undergoing any other psychological therapy
- Have previous experience of a mindfulness-based intervention targeting FND. The intervention tested utilises a mindfulness-based approach, so previous experience of this

would affect the acceptability of the intervention if participants have already engaged in something similar.

- have symptoms of epilepsy and/or loss of consciousness, as treatment sessions will be provided remotely and this impacts on our ability to support and manage risks of individuals that may lose consciousness in a session.
- have symptoms of psychosis (as assessed on the Comprehensive Assessment of At-Risk Mental State, CAARMS), as individuals with both FND and psychosis symptoms would make the sample non-homogenous. Furthermore, individuals with active psychosis are likely to experience more serious adverse reactions and may struggle to engage in the treatment package offered.
- have a diagnosis of Personality Disorder, as they are more likely to experience more serious adverse reactions and may struggle to engage in the treatment package.
- have active plans of self-harm and/or suicide. Potential participants will be asked to complete the risk items on the CORE-OM and will be interviewed around these. This is to ensure the safety of participants engaging in novel therapy and to manage the risks of any potential adverse side-effects of therapy
- Have a history of prior suicide attempts, to manage the risks of causing negative side effects of therapy
- Have any difficulties with alcohol or substance misuse, as this would make the sample non-homogenous. Furthermore, difficulties with alcohol and substance use could impact on ability to engage in the treatment package and also this population could experience more serious adverse reactions.
- Have active symptoms of Post Traumatic Stress Disorder (PTSD) i.e., having current symptoms of nightmares and flashbacks. This population would be more at risk of adverse effects and would make the sample non-homogenous.
- Have symptoms of an eating disorder. This would make the sample non-homogenous and this population would be more at risk of adverse effects.

### **6.3 Recruitment:**

Recruitment:

- Participants will be recruited via advertisements by FND charities. Members of the charities that have an interest in the study will be able to access the information sheet via a link on the website of the charity. Members will be able to register their interest in the study by completing an initial screening questionnaire and providing an email address through which they can be contacted

- The information sheet contains information about the study, the rationale for the study and information about what the treatment will entail and what participants will be asked to complete during the study.
- The initial screening questionnaire aims to screen out individuals who do not meet the eligibility criteria for the study and those who may be more at risk of experiencing adverse effects from the intervention.
- A preliminary meeting will be arranged with the potential participant; this will take place via Microsoft Teams due to the study recruiting from charities across the country. During this meeting, the inclusion/exclusion criteria will be discussed, information in the information sheet will be reiterated and it will be checked that participants have a good understanding of this information. Participants will be given information in both written and verbal format about giving consent to the study. Consent will be taken by the principal researcher using an online form.
- There is no time-frame within which participants must consent and no participant will be enrolled in the study until they have voluntarily given consent.
- Participants will be offered the opportunity to withdraw their consent at any time.
- Participants will also be asked to give consent to be contacted following the study to receive feedback on the results of the study, this is entirely optional for participants. Participants will be supported throughout the process of consenting and there will be no rush or pressure place on participants to give consent until they are ready.
- Following consent to participate in the study, participants will be asked for the contact information for their local GP, social support and local crisis service. This is to inform the generation of a safety plan which will be completed with the participant, which will include an agreed protocol for if something unexpected occurs during therapy. Additionally, a letter will be sent to participants GPs to inform them of their participation in the study.
- Participants meeting all criteria and having completed the safety plan will complete baseline measures: CORE 34, 5 questions assessing FND symptoms, the Screening for Somatoform Symptoms 7 (SOMS-7) and the Work and Social Adjustment Scale (WSAS).
- Following completion of baseline measures, the first remote session to deliver the psychological intervention will be arranged with the participant.

#### **6.4 Participants who withdraw consent [or lose capacity to consent]:**

Participants are able to withdraw consent at any time without giving any reason as participation in the research is voluntary, without their care or legal rights being affected. If a participant wished to withdraw their consent, the principal researcher will request verbal consent for the data already collected to be used for the purposes of the project only and no further data will be collected. If the participant would like to withdraw their full consent, including any previous data collected for the purposes of the project, the principal researcher

will support this in withdrawing any data that has not yet been anonymised. Any data that has been anonymised will not be able to be withdrawn from the study.

